### Contraception

Females of childbearing potential (FCBP) enrolled in this protocol must agree to use two reliable forms of contraception simultaneously or to practice complete abstinence from heterosexual contact during the following time periods related to this study: 1) for at least 28 days before starting study drug; 2) while participating in the study; 3) during dose interruptions; and, 4) for at least 28 days after study treatment discontinuation.

The two methods of reliable contraception must include one highly effective method and one additional effective (barrier) method. FCBP must be referred to a qualified provider of

contraceptive methods if needed. The following are examples of highly effective and additional effective methods of contraception:

Highly effective methods:

- Intrauterine device (IUD)
- Hormonal (birth control pills, injections, implants)
- Tubal ligation
- Partner’s vasectomy

Additional effective methods:

- Male condom
- Diaphragm
- Cervical Cap

*Because of the increased risk of venous thromboembolism in patients with multiple myeloma taking lenalidomide and dexamethasone, combined oral contraceptive pills are not recommended. If a patient is currently using combined oral contraception the patient should switch to one of the effective method listed above. The risk of venous thromboembolism continues for 4 to 6 weeks after discontinuing combined oral contraception. The efficacy of contraceptive steroids may be reduced during co-treatment with dexamethasone.*

Implants and levonorgestrel-releasing intrauterine systems are associated with an increased risk of infection at the time of insertion and irregular vaginal bleeding. Prophylactic antibiotics should be considered particularly in patients with neutropenia.

#### Pregnancy testing

Medically supervised pregnancy tests with a minimum sensitivity of 50 mIU/mL must be performed for females of childbearing potential, including females of childbearing potential who commit to complete abstinence, as outlined below.

#### **Before starting study drug**

*Female Patients:*

FCBP must have two negative pregnancy tests (minimum sensitivity of 50mIU/mL) prior to starting study drug. The first pregnancy test must be performed within 10 to 14 days prior to the start of study drug and the second pregnancy test must be performed within 24 hours prior to the start of study drug (prescriptions must be filled within 7 days as required by the Revlimid REMS® program). The patient may not receive study drug until the study doctor has verified that the results of these pregnancy tests are negative.

*Male Patients:*

Must practice complete abstinence or agree to use a condom during sexual contact with a pregnant female or a female of childbearing potential while participating in the study, during

dose interruptions and for at least 28 days following study drug discontinuation, even if he has undergone a successful vasectomy.

### **During study participation and for 28 days following study drug discontinuation**

#### *Female Patients:*

- FCBP with regular or no menstrual cycles must agree to have pregnancy tests weekly for the first 28 days of study participation and then every 28 days while on study, at study discontinuation, and at day 28 following study drug discontinuation. If menstrual cycles are irregular, the pregnancy testing must occur weekly for the first 28 days and then every 14 days while on study, at study discontinuation, and at days 14 and 28 following study drug discontinuation.
- At each visit, the Investigator must confirm with the FCBP that she is continuing to use two reliable methods of birth control.
- Counseling about pregnancy precautions and the potential risks of fetal exposure must be conducted at a minimum of every 28 days.
- If pregnancy or a positive pregnancy test does occur in a study patient, study drug must be immediately discontinued.
- Pregnancy testing and counseling must be performed if a patient misses her period or if her pregnancy test or her menstrual bleeding is abnormal. Study treatment must be discontinued during this evaluation.
- Females must agree to abstain from breastfeeding during study participation and for at least 28 days after study drug discontinuation.

#### *Male Patients:*

- Counseling about the requirement for complete abstinence or condom use during sexual contact with a pregnant female or a female of childbearing potential and the potential risks of fetal exposure to lenalidomide must be conducted at a minimum of every 28 days.
- If pregnancy or a positive pregnancy test does occur in the partner of a male study patient during study participation, the investigator must be notified immediately.

#### Additional precautions

- Patients should be instructed never to give this medicinal product to another person and to return any unused capsules to the study doctor at the end of treatment.
- Female patients should not donate blood during treatment and for at least 28 days following discontinuation of lenalidomide.
- Male patients should not donate blood, semen or sperm during treatment or for at least 28 days following discontinuation of lenalidomide.
- Only enough study drug for 28 days or one cycle of therapy (whichever is shorter) may be dispensed with each cycle of therapy.

**APPENDIX C**  
**REVLIMID REMS® PROGRAM**

## APPENDIX C

### Revlimid Overview Revlimid REMS® for Study Participants

#### **Revlimid REMS® description:**

A program that allows patients enrolled in authorized clinical trials access to free Revlimid® through the Revlimid REMS® program.

#### **Access to the Revlimid REMS® Program:**

- 1. All physicians must be registered prescribers of Revlimid® in the Revlimid REMS® Program All clinical sites must have access to the Revlimid REMS® software to enroll patients in the Revlimid REMS® program**
  - 1) Prescriber submits Registration Form via fax or RevAssist® Online (*RAO* for Revlimid) to Celgene Customer Care.
  - 2) Prescriber is registered within 15 minutes.
  - 3) Registration confirmation fax is sent to prescriber's office via fax. (For RAO, the confirmation notification is displayed on the screen immediately)
  - 4) Starter Kit is sent to prescriber's office (overnight). The starter kit will contain the following:
    - Instructions For Prescribers
    - Patient Resource Packs
    - Guide to English and Non-English Materials
    - Computer software used to generate Patient-Physician Agreement Forms (PPAF)
- 2. All studies must have an FDA letter of IND exemption or an active IND, active IRB approval and Celgene required regulatory documents.**
- 3. Patients must sign the research specific IRB-approved informed consent and be enrolled in a Celgene-approved Medical Affairs clinical trial using Revlimid®**
- 4. Celgene Customer Care Center must be contacted to confirm if a patient needs to be registered by calling [name].**
- 5. Patients must also sign the appropriate PPAF form and follow all the procedures of the Revlimid REMS® Program**
  - 1) Patient and Prescriber complete the PPAF together.
  - 2) The form is faxed to Celgene Customer Care or submitted electronically through *RAO*.
  - 3) Patient is registered within 15 minutes.
  - 4) Confirmation fax is sent to prescribing office notifying them that the patient is now registered. For RAO, the confirmation notification is displayed on the screen immediately.
- 6. Patients and prescribers must take the phone surveys as required by the Revlimid REMS® Program (The PPAF generated for the patient determines which phone survey**

questions will be asked.) **An authorization number is provided at the completion of the phone survey, the authorization number should be noted on the prescription form.**

Patient Survey requirements:

- For men: Do not need to call Celgene the first month but must call monthly starting the second month.
- For females of non - child bearing potential: Must call for the first month and then call every 6 months after.
- For females of child bearing potential: Must call for the first month and then every month after.

#### **Prescribing Revlimid® in the Revlimid REMS® program**

- Celgene Medical Affairs Operations will activate the study with Biologics upon receipt of all required regulatory documents.
- Biologics will not dispense or ship Revlimid® prior to Celgene's notification of activation.
- Prescription information **MUST BE** entered using **the BMT CTN 0702 Revlimid REMS® study specific electronic prescription form**. This form can be found on the BMT CTN SharePoint website (<https://bmtctnsp.net>)
- **An authorization number** must be on the prescription form at the time of faxing.
- Prescriptions for Revlimid® must be sent to Biologics Clinical Trial Division at the following [contact]
- Only a 28-day supply of Revlimid® may be provided per cycle sent to the actual address noted on the **Revlimid REMS® electronic prescription form**.
- **Biologics will verify the authorization number** and complete the patient counseling.

#### **Protocol compliance and drug return**

- Patients will be provided with instructions from Biologics with each new dispense on the procedures for return of any un-used Revlimid® capsules. (Patients will be instructed to call the 1-800 number to request a prepaid return envelope as per the commercial drug return procedures)
- Sites may request that patients maintain a diary and/or to bring their bottles in for a pill count at each visit in order to review “**patient compliance.**” However, they are not responsible for “**drug accountability.**”

## IMPORTANT INFORMATION ABOUT RevAssist®

---

- To avoid fetal exposure REVLIMID®(lenalidomide) is only available under a special restricted distribution program called Revlimid REMS®
- Only prescribers registered with Revlimid REMS® can prescribe REVLIMID®(lenalidomide)
- Only Revlimid REMS®contract pharmacies can dispense REVLIMID®(lenalidomide)
- In order to receive REVLIMID® (lenalidomide), patients must enroll in Revlimid REMS®and agree to comply with the requirements of the Revlimid REMS® program
- Information about REVLIMID®(lenalidomide) and the Revlimid REMS® program can be obtained by calling the Celgene Customer Care Center toll-free at [name], or at [www. REVLIMID.com](http://www.REVLIMID.com)

## How to Fill a REVLIMID® (lenalidomide) Prescription

---

1. Healthcare provider (HCP) instructs patient to complete patient survey
2. HCP completes survey
3. HCP completes patient prescription form
4. HCP obtains Revlimid REMS®authorization number
5. HCP provides authorization number on patient prescription form
6. HCP faxes form, including prescription
7. HCP advises patient that a representative from a Revlimid REMS® contract pharmacy will contact them
8. Revlimid REMS® contract pharmacy conducts patient education
9. Revlimid REMS® contract pharmacy calls for confirmation number
10. Revlimid REMS® contract pharmacy ships REVLIMID® to patient with the FDA-approved MEDICATION GUIDE

**APPENDIX E**  
**RESEARCH SAMPLES**

## **OPTIONAL RESEARCH SPECIMENS**

Patients consenting to the optional future research will have blood samples collected for future research supporting this protocol. All research sample aliquots will be given unique bar code designations that cannot be linked back to the participant's name or other identifying information. Laboratory test results, clinical information, etc., associated with the coded samples are provided to the Investigator only after completion of the protocol. Samples sent to researchers cannot be linked with any remaining samples at the repository.

Patient samples will be collected both prior to the initiation of long-term follow-up and at disease progression. All research samples will be collected and shipped same-day to the BMT CTN Repository for processing and sample aliquot storage. Sample collection and shipping procedures are detailed in the BMT CTN 0702 Long-Term Follow-Up Laboratory Sample Guide.

Under current guidelines of the BMT CTN, any request to utilize samples from the biorepository is first reviewed by the protocol team. Upon approval, the request is then reviewed by the BMT CTN Biomarkers Committee, which advises the Executive or Steering Committee. Following approval by these boards, samples are then released from the BMT CTN biorepository.

	Type of Sample	Type of Processing	Dates Samples Obtained	Shipping Specifications	Storage Location
Patient Research Peripheral Blood Specimen (Serum)	6 mL peripheral blood	Collect blood sample in a Red/Gray Top BD SST™ Tube with Silica Clot Activator & Polymer Gel. Let sample sit upright in rack for 30 minutes. Centrifuge for 10 minutes. Gel barrier will form separating the serum specimen from clot. Prepare tube for transport along with other research samples.	Prior to initiation of long-term follow-up and at disease progression.	Serum blood tube will be shipped at ambient temperature on the day of collection, to the BMT CTN Research Repository by priority overnight FED EX delivery for processing and final frozen storage of serum aliquots. Guidelines for specimen handling and shipment to the BMT CTN Central Processing Laboratory/BMT CTN Research Repository are detailed in the 0702 Long-Term Follow-Up Laboratory Sample Guide	BMT CTN Research Repository
Patient Research Peripheral Blood Specimen (Plasma)	5 mL peripheral blood	Collect blood sample in a 5 mL fill, white top plastic Greiner Vacuette® PST tube. Gently mix sample with EDTA by inverting the tube 8-10 times. Centrifuge for 10 minutes. Gel barrier will form separating the plasma specimen from cells. Prepare tube for transport along with other research samples.	Prior to initiation of long-term follow-up and at disease progression..	Plasma blood tube will be shipped at ambient temperature on the day of collection, to the BMT CTN Research Repository by priority overnight FED EX delivery for processing and final frozen storage of serum aliquots. Guidelines for specimen handling and shipment to the BMT CTN Central Processing Laboratory/ Research Repository is detailed in the 0702 Long-Term Follow-Up Laboratory Sample Guide	BMT CTN Research Repository

	Type of Sample	Type of Processing	Dates Samples Obtained	Shipping Specifications	Storage Location
Patient Research Peripheral Blood Specimen (PBMC)	20 mL peripheral blood	Collect peripheral blood sample in two 10 mL fill, green top plastic BD Vacutainer ® tube, containing Sodium-Heparin anticoagulant. Gently mix sample by inversion 8-10 times to mix sample well with heparin anticoagulant.  No additional sample processing is required.	Prior to initiation of long-term follow-up therapy and at disease progression.	Peripheral blood tubes will be shipped at ambient temperature on the day of collection, to the BMT CTN Research Repository by priority overnight FED EX delivery for processing and final frozen storage of isolated viable PBMC aliquots. Guidelines for specimen handling and shipment to the BMT CTN Central Processing Laboratory/BMT CTN Research Repository is detailed in the 0702 Long-Term Follow-Up Laboratory Sample Guide	BMT CTN Research Repository

**APPENDIX F**

**ADVERSE EVENTS**

**APPENDIX F****ADVERSE EVENTS**

Selected expected serious AEs (Table F-1) and grade 3-5 unexpected AEs according to the National Cancer Institute Common Terminology Criteria for Adverse Events (CTCAE) version 4.0 require expedited reporting with an Individual Case Safety Report (ICSR) through completion of the Adverse Event Forms. Additionally, selected AEs of interest (Table F-2) will require expedited reporting through an ICSR, if they fulfill serious criteria and occur after the administration of lenalidomide. Refer to Chapter 4 regarding reporting of SPMs and other reporting requirements.

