### 1.3.Second Primary Malignancies

The lenalidomide group in CALGB/ECOG 100104 (BMT CTN 0704) had an increased incidence of hematologic toxicities (primarily neutropenia) and an increase in second primary malignancies (SPM). There were 8/231(3.5%) hematologic malignancies, primarily Acute Myeloid Leukemia/Myelodysplastic Syndrome (AML/MDS) in lenalidomide group patients versus 1/229 (0.4%) in placebo group patients. There were 10/231 (4.3%) versus 5 (2.1%) solid tumors in lenalidomide group and placebo group patients respectively, and 4/231 (1.7%) versus 3/229 (1.3%) non-melanoma skin cancers. In the 2013 update, one AML was reported in the lenalidomide arm (total 9/231 hematologic malignancies) and one case of ALL and MDS in two placebo arm patients who crossed over to lenalidomide. One solid tumor (renal cell carcinoma) was reported in another cross over patient and 4 non-melanoma skin cancers were reported; 3 in

the lenalidomide arm and one in a cross over placebo patient. The cumulative incidence risk (CIR) for the development of SPM was greater for the lenalidomide group when compared to the placebo group ( $p < 0.008$ ). The CIR of progressive disease ( $p < 0.001$ ) or death ( $p < 0.002$ ) were greater for the placebo group when compared to the lenalidomide group. When including deaths, progressions and SPMs as events, the median EFS was 43 months for the lenalidomide group and 27 months for the placebo group ( $P < 0.001$ ).

The placebo group patients in the IFM 05-02 study did not cross over to receive lenalidomide at un-blinding. The lenalidomide group had an increased incidence of hematologic toxicities (primarily neutropenia) and an increase in SPMs. There were 13/306 (4.2%) hematologic malignancies, (primarily Acute Lymphoblastic Leukemia (ALL) and Hodgkin Lymphoma and AML/MDS) in lenalidomide group patients versus 5/302 (primarily AML/MDS only) in placebo group patients. There were 10/306 (3.3%) versus 4/302 (1.3%) solid tumors in the lenalidomide group and placebo group patients respectively and 5/306 (1.6%) versus 3/302 (1.0%) non-melanoma skin cancers. When including deaths, progressions and SPMs as events, the median EFS was 40 months for the lenalidomide group and 23 months for the placebo group ( $P < 0.001$ ). An updated analysis was recently presented.

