## 2.6. Participant Risks

### 2.6.1. Lenalidomide

Common toxicities described for lenalidomide include:

- Neurologic: Somnolence, dizziness, headache, confusion, tremor, loss of co-ordination, asthenia, paresthesia, numbness, and leukoencephalopathy (radiographic findings).
- Hematologic: anemia, neutropenia, leucopenia, lymphopenia and thrombocytopenia; thromboembolic events (deep vein thrombosis and pulmonary embolism).
- Gastrointestinal: Constipation, dehydration, dry mouth, diarrhea, dyspepsia, nausea, vomiting and stomatitis.
- Constitutional: Weakness, insomnia, rigors, chills, sweating, weight loss and fever.
- Reproductive: teratogenicity and miscarriage.
- Musculoskeletal: arthralgia, back/neck pain, joint pain, muscle cramp and weakness.
- Cardiac: hypotension.
- Dermatologic: rash, dry skin, itching.
- Endocrine: hypothyroidism.
- Infection.
- Pulmonary: cough, dyspnea.
- Metabolic: hypokalemia, liver damage.
- Renal: increased creatinine, renal failure.

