### 4.3. Adverse Event Reporting

#### 4.3.1. Unexpected, Grades 3-5 Adverse Events

Reporting of Adverse Events (AE) in the long-term follow-up protocol will follow the same mechanism as the BMT CTN 0702 parent clinical trial for patients receiving long-term lenalidomide maintenance therapy. AEs will be reported according to the BMT CTN Manual of Procedures. The BMT CTN Data and Safety Monitoring Board (DSMB) will be responsible for the safety and oversight of this long-term follow-up protocol. Unexpected, grades 3-5 adverse events will be reported through the expedited AE reporting system in AdvantageEDC using NCI's Common Terminology Criteria for Adverse Events (CTCAE) Version 4.0. Unexpected, grade 4-5 AEs must be reported within 24 hours of knowledge of the event. Unexpected, grade 3 AEs must be reported within three business days of knowledge of the event.

The descriptions and grading scales found in the NCI Common Terminology Criteria for Adverse Events (CTCAE) Version 4.0 will be utilized for AE reporting and can be found at [http://evs.nci.nih.gov/ftp1/CTCAE/CTCAE\\_4.03\\_2010-06-14\\_QuickReference\\_5x7.pdf](http://evs.nci.nih.gov/ftp1/CTCAE/CTCAE_4.03_2010-06-14_QuickReference_5x7.pdf).

Selected expected serious AEs (Appendix F - Table F-1) require expedited reporting with an Individual Case Safety Report (ICSR). Additionally, selected AEs of interest (Appendix F - Table F-2) will require expedited reporting through an ICSR, if they fulfill serious criteria according to the Code of Federal Regulations Title 21 (21 CFR 312.32) and occur after the administration of lenalidomide and up to 30 days after the permanent discontinuation of lenalidomide. See Appendix F for additional details on expedited reporting.

The aforementioned adverse event reporting criteria are for patients who receive long-term lenalidomide maintenance therapy. Patients not eligible for receiving long-term lenalidomide maintenance therapy or patients who have permanently discontinued lenalidomide maintenance will not require reporting of unexpected grades 3-5 adverse events or ICSRs with the exception of second primary malignancies as noted in 4.3.2. All patients will be required to report deaths as noted in section 4.3.3.

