 Serious Adverse events are defined by the 21 CFR (312.32a): AE that results in death, requires hospitalization, persistent or significant disability or incapacity, congenital anomaly, that is life threatening or considered as medically important.

**TABLE F-2: EXPECTED ADVERSE EVENTS OF INTEREST THAT WILL REQUIRE EXPEDITED REPORTING IF THEY MEET SERIOUS ADVERSE EVENT CRITERIA AND OCCUR AFTER THE INITIATION OF LENALIDOMIDE AND THROUGH 28 DAYS AFTER THE DISCONTINUATION OF LENALIDOMIDE**

Adverse Event	Seriousness or Capture Method 	Collection Form
AUDITORY/EAR		
Hearing loss	SAE	ICSR
CARDIAC		
Atrial fibrillation	SAE	ICSR
Atrial flutter	SAE	ICSR
COAGULATION		
Deep vein thrombosis	SAE	ICSR
Pulmonary emboli 	SAE	ICSR
HEMORRHAGE		
Hemorrhage, Gastrointestinal	SAE	ICSR
Hemorrhage, Pulmonary	SAE	ICSR
METABOLIC/LABORATORY		
Elevation of ALT $\geq 2.5x$ ULN	SAE	ICSR
Elevation of AST $\geq 2.5x$ ULN	SAE	ICSR
Elevation of Bilirubin $\geq 3x$ ULN	SAE	ICSR
MUSCULOSCELETAL/SOFT TISSUE		
Muscular weakness	SAE	ICSR
NEUROLOGY		
Neurology – Peripheral neuropathy	SAE	ICSR

Adverse Event	Seriousness or Capture Method	Collection Form
Neuropathy: Motor	SAE	ICSR
Neuropathy: Sensory	SAE	ICSR
Syncope (fainting)	SAE	ICSR
OCULAR/VISUAL		
Vision – Blurred vision	SAE	ICSR
PAIN		
Pain – Neuralgia	SAE	ICSR
INFECTION		
Febrile neutropenia	SAE	ICSR
DEATH		
Sudden death	SAE	ICSR
OTHER		
Second malignancies	SAE	ICSR

 Serious Adverse events as defined by the 21 CFR (312.32a): AE that results in death, requires hospitalization, persistent or significant disability or incapacity, congenital anomaly, that is life threatening or considered as medically important.

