1.5 Response Variables and Data Collection Time Points

Participants are evaluated for the primary endpoint of progression-free survival (death, disease progression, initiation of non-protocol myeloma therapy) and for the following secondary endpoints:

- Overall survival
- Event-free survival (no progression, death, or SPM)
- Incidence of SPM
- Unexpected grades 3-5 adverse events
- Health quality of life

Patients have visits every six months until death, progression, withdrawal of consent, or the end of the study.

Participants who receive long-term lenalidomide maintenance therapy are required to report unexpected grades 3-5 adverse events until the patient progresses or until 28 days from their last dose of lenalidomide. These require expedited reporting within 24 hours – 3 business days of the site's knowledge of the event, depending on the type of event. The protocol specifies additional rules for reporting requirements of AEs after an SPM depending on the treatment received for the SPM, and for reporting serious expected adverse events and selected AEs of interest.

Participants who do not receive lenalidomide maintenance or have permanently discontinued lenalidomide maintenance not required to report adverse events except for SPMs.

For all participants on 07LT, SPMs must be reported within three business days of knowledge of the event and deaths must be reported within 24 hours of knowledge of the participant's death. Non-melanoma skin cancers are not required to be reported.

Health quality of life surveys are completed at visits corresponding to 5, 6, and 7 years from original randomization on 0702.

2. General Statistical Considerations

Unless stated otherwise:

- For continuous outcomes, descriptive statistics will include the number of subjects (n), mean, standard deviation, median, minimum and maximum.
- For categorical outcomes, frequencies and percentages will be displayed for categorical data.
- All statistical comparisons made using 2-sided pairwise tests will be compared to an α =0.05/3 significance level.

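### Apart from febrile neutropenia, serious infections and cytopenias on extended lenalidomide are on neither reporting list, and the SAP tabulates only unexpected grade 3-5 events

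*Protocol*

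**What the plan says.** Protocol Section 4.3.1 and Appendix F set the adverse event rules for patients taking lenalidomide on 07LT. Section 4.3.1 says "Unexpected, grades 3-5 adverse events will be reported through the expedited AE reporting system in AdvantageEDC". Appendix F extends individual case safety reports to "Selected expected serious AEs (Table F-1) and grade 3-5 unexpected AEs", and to the Table F-2 events when they are serious and follow lenalidomide. SAP 1.5 matches: "Participants who receive long-term lenalidomide maintenance therapy are required to report unexpected grades 3-5 adverse events". SAP 2.7.2 restates the same three routes.

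Section 2.6.1 opens with "Common toxicities described for lenalidomide include" and then lists, among others, "Hematologic: anemia, neutropenia, leucopenia, lymphopenia and thrombocytopenia". Infection is a separate entry in the same list. In the two appendix tables the only matching row is "Febrile neutropenia", under the infection heading of Table F-2.

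For analysis, SAP 2.7.2 and 4.2 plan to tabulate unexpected grade 3-5 events. Exhibit 07LT-9A does this for participants who started lenalidomide on 07LT and Exhibit 07LT-9B for those who did not.

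**The concern.** The protocol itself treats blood counts as central to the safety of this drug. Section 1.3 reports neutropenia as the main excess hematologic toxicity in both background trials it describes, and Table 2.4.2c bases holds, reductions and discontinuation on ANC and platelets. Table F-2 exists to pick up expected toxicities when they become serious. It includes the two thromboembolic events that share a bullet with the cytopenias in Section 2.6.1, but no cytopenia other than febrile neutropenia. Less central events, such as hearing loss and cranial palsy, are on the lists.

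The study gives lenalidomide beyond three years, and the DSMB reviews safety about every six months (Section 5.5). If serious infections and cytopenias fall outside the stated rules, or are reported but never tabulated, the summary of extended treatment will say little about them. Because the supplied text does not define *unexpected*, sites may also classify the same event differently, which would make reporting uneven.

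**Working it through.** No formula or event figure in the plan bears on this. The check is a count of the lists and a trace of example events through the rules.

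**1. Count of listed terms (Appendix F)**
- Table F-1: 49 entries. Pulmonary hypertension appears twice, so 49 − 1 = 48 distinct.
- Table F-2: 20 entries. Six are also in F-1 (three neuropathy terms, syncope, sudden death, second malignancies), so 20 − 6 = 14 new.
- Total distinct: 48 + 14 = 62.

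**2. Match to Section 2.6.1**
- Table F-1: 0 infection or cytopenia rows. Its lung-infiltrate row is restricted to cases without infection. Diverticulitis is listed under gastrointestinal events and is counted there.
- Table F-2: 1 row, febrile neutropenia.
- Of the five cytopenias in Section 2.6.1, none has a row of its own; neutropenia appears only when febrile.

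**3. Trace of two events not listed.** Take (a) a hospitalised pneumonia with a normal neutrophil count, after which lenalidomide continues, and (b) a life-threatening thrombocytopenia without bleeding, managed by a hold and restart. Suppose the site regards both as expected because Section 2.6.1 lists them.
- Unexpected grade 3-5 route: closed by that judgement.
- Table F-1 and Table F-2 routes: no matching row.
- Visit schedule: Tables 4.4.1 and 4.4.2 have no toxicity or infection item. These are schedules, not case report forms, so they do not settle what the forms ask.
- Blood counts: Section 4.4.2 requires a CBC before each monthly supply, but does not say that results become study data.
- Discontinuation reasons (SAP 3.2, Supplemental Exhibit 07LT-3): cover permanent stops only, so neither event appears.
- CIBMTR data: SAP 4.2 excludes them from the adverse event analysis.

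**4. Trace of one event that is listed.** A serious deep vein thrombosis on lenalidomide is in Table F-2, whose title calls its events expected. It is therefore reported. Exhibit 07LT-9A is limited to unexpected events, so it does not appear there either. The tabulation gap is thus wider than infections and cytopenias. Of the 62 terms, second malignancies have Exhibits 07LT-7 and 07LT-8, and sudden death would fall within Supplemental Exhibit 07LT-4. The other 62 − 2 = 60 have no planned table when classed as expected.

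**5. Cross-references.** Sections 4.3.1.1 and 4.3.2.1 define reportable events by an Appendix K, but the appendix list ends at G. Section 4.3.2.1 also points to a Section 4.2.3 for adverse event reporting, and Chapter 4 has no such section.

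**The case against.** A reader might infer that serious infections and cytopenias are never reported unless fatal, so that neither the DSMB nor the final report can see them. The documents do not support that.

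- Febrile neutropenia is in Table F-2. Some severe presentations of sepsis or thrombocytopenia could also be reported through listed terms such as DIC, ARDS or hemorrhage.
- Appendix F governs expedited reports. Section 4.3.1 sends adverse event reporting to the BMT CTN Manual of Procedures and the parent-trial mechanism. Neither is supplied, so routine collection can be neither confirmed nor excluded.
- *Expected* is an inference from a list of common toxicities. A site could judge life-threatening sepsis unexpected and report it within 24 hours.
- A toxicity that permanently ends lenalidomide can appear as a discontinuation reason.
- The DSMB's material is not stated to be limited to expedited reports.

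It would also go too far to call infection a main dose-limiting toxicity: it has no row of its own in the dose-modification tables. That description fits the cytopenias only.

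The sponsor can add that listing *selected* events and choosing unexpected grade 3-5 events as the safety endpoint were deliberate.

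All of this limits the claim about collection. It does not answer the tabulation gap, which lies within the SAP. A single SAP 2.7.2 sentence promises summaries by type and severity without repeating *unexpected*, but it directly follows the sentence confined to unexpected events, and SAP 4.2 and both exhibits keep that restriction.

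**Conclusion.** The point holds in two parts of different strength.

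- **Reporting (conditional).** If sites treat the Section 2.6.1 toxicities as expected, the protocol and SAP as supplied state no rule for reporting a non-fatal serious infection, or a serious cytopenia without fever, on 07LT lenalidomide. An outside source may close this gap, but the reader cannot tell from these documents.
- **Tabulation (not dependent on outside sources).** Even when such events are collected, or are already in Tables F-1 or F-2, the planned adverse event tables omit them if they are classed as expected.

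In size, 1 of 62 listed terms covers these toxicities, and no planned adverse event table covers expected serious events. The number of patients or events affected cannot be derived: the documents give no count of patients on 07LT lenalidomide, no exposure time and no event rates. This is an inexpensive improvement to safety reporting and does not affect the efficacy comparisons.

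**What to change.** 1. Add serious-only rows to Table F-2 for infection, neutropenia, thrombocytopenia and anemia, on the existing adverse event forms and in the existing F-2 window. If the parent-trial mechanism already collects these events, cite that source in Section 4.3.1 instead. The window itself needs reconciling: the Table F-2 title gives 28 days after discontinuation, while Section 4.3.1 and SAP 2.7.2 give up to 30.
2. Add to SAP 2.7.2 and 4.2 a table of expected serious events (the F-1 and F-2 terms, including the new rows) by treatment arm for 07LT participants on lenalidomide, and include it in the DSMB reports.
3. Reconcile the Appendix K references in Sections 4.3.1.1 and 4.3.2.1 with Appendix F, and correct the reference to Section 4.2.3.

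The cost is a short amendment, one SAP table and a modest number of extra case reports, which the serious-only condition limits. No visit, test, dose, hold or stopping rule changes.
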